5.4 Justification

Control and prevent inflammation is one of the main concerns of the ophthalmologist surgeon to achieve optimal results after surgery.

Steroids are the drugs of first choice for the control of inflammation due to its broad anti-inflammatory activity and its safety profile.

PRO-145 is a formulation of 0.05% DFBA in ophthalmic emulsion, developed by Sophia Laboratories, S.A. of C.V. which has demonstrated an acceptable safety profile in preclinical and clinical phase I studies, as well as a bioavailability in animal models similar to that reported for Durezol®. With this background, a phase III clinical study is required to verify the efficacy profile of PRO-145.

5.5 Objectives and hypothesis

5.5.1 General purpose

To evaluate the efficacy of the ophthalmic emulsion PRO-145 in the treatment of inflammation and pain after phacoemulsification.

5.5.2 Specific objectives

- Evaluate the efficacy of PRO-145 through the elimination of anterior chamber cellularity (CCA) at the final visit.
- Evaluate the efficacy of prednisolone acetate 1% by means of the elimination of CCA in the final visit

5.5.3 Secondary objectives

- Evaluate the efficacy of PRO-145 through the decrease of CCA in the ordinal scale during visits
- Evaluate the efficacy of PRO-145 by decreasing the central thickness of the retina (GCR).
- Evaluate the efficacy of PRO-145 by decreasing clinical corneal edema.
- Evaluate the efficacy of PRO-145 through the reduction of conjunctival hyperemia.
- Evaluate the efficacy of PRO-145 by means of the decrease of flare.
- Evaluate the efficacy of PRO-145 in reducing symptoms: pain and photophobia.
- To evaluate the tolerability of PRO-145 by means of the interrogation of ocular symptomatology post-stiffening.

- Evaluate the safety of PRO-145 through the CV, the PIO and the incidence of EA
- To evaluate the efficacy of prednisolone acetate 1% by means of the decrease of CCA in the ordinal scale during visits
- Evaluate the efficacy of prednisolone acetate 1% by means of the decrease in GCR.
- Evaluate the efficacy of prednisolone acetate 1% by means of the decrease of clinical corneal edema.
- Evaluate the efficacy of prednisolone acetate 1% by means of the reduction of conjunctival hyperemia.
- Evaluate the efficacy of prednisolone acetate 1% by means of the decrease in flare.
- Evaluate the efficacy of prednisolone acetate 1% in reducing symptoms: pain and photophobia.
- To assess the tolerability of prednisolone acetate 1% by means of the interrogation of ocular symptomatology postinstillation.
- Evaluate the safety of prednisolone acetate 1% by means of the CV, the PIO and the incidence of EA.

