surgical techniques, more advanced phacoemulsification machines, the introduction of femtosecond laser-assisted cataract surgery (known as FLACS, after its acronym in English femtosecond laser-assisted cataract surgery) and the evolution of Intraocular lenses (LIO), cataract surgery has been allowed to be consistently safer and with a high predictability of good visual rehabilitation, often not requiring visual correction by means of aerial lenses. This has led to the AV to indicate cataract surgery in industrialized countries from 20/30 or less. [10] [11]

In 2014 it was estimated that 2 million cataract surgeries were performed in the United States of America (USA). [12] For 2015, 3.6 million surgeries were estimated in the USA and more than 20 million worldwide. [13] In Mexico, it is estimated that the rate of cataract surgery is 1,530 surgeries per million inhabitants. [14]

Like any other type of surgery, cataract surgery induces an inflammatory response despite advances in surgical technique. Inflammation after cataract surgery continues to be a common cause of patient discomfort, delayed recovery and decreased visual outcome due to posterior synechiae, uveitis, macular edema and secondary glaucoma, among other conditions. [15] [16] [17]

The physical trauma associated with cataract surgery, including the alteration of the blood-brain barrier, induces an inflammatory response and the release of mediators of inflammation such as prostaglandins and leukotrienes (See Figure 1). Prostaglandins are released naturally from the iris and ciliary body and migrate to the retina, after cataract surgery. [18] The inflammatory response, in turn, can activate the cascade of the immune response, releasing additional neutrophils, macrophages, T lymphocytes and mediators of inflammation. [18] [19] [20]

Inflammation after cataract surgery presents with signs such as flare, cellularity in the anterior chamber, conjunctival hyperemia, edema, leukocyte migration, proliferation of fibroblasts and scarring. [21] [22] Persistent inflammation causes discomfort to the patient, increased rate of macular edema and compromises the visual result. [15] [16] [22] Potential complications of postoperative inflammation without treatment include pain, photophobia, synechiae, cellular precipitates, uveitis, increased intraocular pressure (IOP), and glaucoma. [23] Because of this, the management of postoperative inflammation is mandatory in modern cataract surgery. [17]

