6.2 Eligibility criteria.

6.2.1 Inclusion criteria.

- Signed informed consent.
- Age ≥ 18 years.
- Both sexes.
- Postoperative cataract surgery by phacoemulsification.
 - o That they have met the criteria for phacoemulsification and a classification of the LOCS III cataract of NO ≥ 2 and NC ≥ 2 .

6.2.2 Exclusion criteria.

6.2.2.1 General criteria.

- Pregnant women, lactating or planning to get pregnant.
- Women of reproductive age and who do not have a hormonal contraceptive method, intrauterine device or bilateral tubal obstruction.
- Participation in another clinical research study ≤ 30 days before the baseline visit.
- Have previously participated in this same study with the contralateral eye.
- That they can not comply with their attendance at appointments or with all the requirements of the protocol.

6.2.2.2 Medical and therapeutic criteria.

- Surgery in both eyes in the same surgical shift.
 - Time > 24 hours after having surgery.
 - LIO placement outside the bag.
 - Presentation of rupture of the posterior capsule, with or without the presence of vitreous.
 - Carrying out an iridectomy, or lesion of the pupillary sphincter during phacoemulsification surgery.
 - Scheduled for surgical intervention in the contralateral eye during the study period.
 - History of glaucoma or ocular hypertension.
 - History of increased PIO with the use of steroids.
 - PIO ≥ 24 .
 - History of uveitis.
 - Presence of corneal abrasion or corneal ulceration in the study eye.
 - Use of steroids or topical NSAIDs, 24 hours prior to surgery and until the start of instillation of investigational drugs.
 - Use of anticoagulants, systemic steroids or immunomodulators in the last two weeks
 - Periocular injection of any steroid in the study eye 4 weeks before the start of the instillation of the investigational drugs.
 - Use of storage steroids 2 months prior to the start of instillation of investigational drugs.
 - Presence or suspicion of keratitis and / or viral, bacterial or fungal conjunctivitis.
 - Presence or suspicion of endophthalmitis.
 - Presence or suspicion of toxic syndrome of the anterior segment.
 - Severe corneal edema that does not allow assessment of the anterior chamber
 - Macular diseases.
-
- Diabetes Mellitus with A1C $\geq 6.5\%$ (48 mmol / mol) or fasting glucose (no caloric intake by ≥ 8 hours) of ≥ 126 mg / dL (7.0 mmol / L).
 - Any disease or condition that requires the use of topical or systemic NSAIDs during the time of intervention.

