By means of optical coherence tomography (OCT) the GCR will be measured; Because this is a multicenter study it is not feasible to standardize the brand and model of the OCT to be used, it will allow the use of OCT Stratus (Carl Zeiss), Cirrus (Carl Zeiss), Spectralis (Heidelberg Engineering) with the minimum requirement that the baseline and final OCT are performed with the same OCT, with the same protocol and these characteristics are recorded in the clinical note and in the CRF, together with the central average.

6.4.3.6 Tonometry.

Tonometry is the objective measure of PIO, based primarily on the force required to flatten the cornea, or the degree of corneal indentation produced by a fixed force. Goldman's tonometry is based on the Imbert-Fick principle. [71]

The tonometry will be carried out, after instillation of the topical anesthetic, with fluorescein and the use of the cobalt blue filter (after the evaluation of the surface staining). There will be 2 shots and the average will be calculated, which will be recorded in the clinical file. The average will be registered in the CRF.

6.4.4 Measurement time.

- Measurements at the baseline visit

- Biomicroscopy
- Visual ability
- History of symptomatology
- OCT
- Tonometry
- Evaluation of adverse events
- Measurements in visit 1 and 2
- Biomicroscopy
- Visual ability
- Evaluation of adverse events
- History of symptomatology
- Tonometry
- Measurements in final visit
- Biomicroscopy
- Visual ability
- Adverse event evaluation
- History of symptomatology
- OCT
- Tonometry
- Measurements on security call
- Evaluation of adverse events

6.5 Schedule and study diagram.

The **baseline visit** will be considered on day 1 of the study and should be within the first 24 postoperative hours, the IP will indicate the subject to start the application of the investigational products that same day. If necessary, adjust the scheme so that it complies with the 4 applications of day 1; however, in the event that during the opening hours it is not feasible to adjust the 4 applications, the IP will indicate the application of at least 2 instillations, with a minimum of 2 hours between them.

Visit 1 will be performed in relation to the start of treatment on day 7 with a window period of ± 2 days.

The **visit 2 and final** will be made on days 14 and 29, respectively, with a window period of ± 2 days for visit 2 and + 3 days for the final.

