- Delivery of medication: Refers to the delivery of the medication to the study patient, by the research center. It will be done according to sections 6.3.1 Managed treatments and 6.3.4.1 Delivery and reception. After each medication delivery, a training or re-training of the application of the study medication will be carried out.
- Biomicroscopy: see 6.4.3.1 Biomicroscopy
- Visual capacity: see 6.4.3.2 Visual capacity
- History of symptomatology: see 6.4.3.4 History of symptomatology
- OCT: see 6.4.3.5 Optical coherence tomography. For this visit, the OCT can be done in a window period of 48 hours.
- Tonometry: see 6.4.3.6 Tonometry

- Evaluation of concomitant medications: refers to the interrogation performed by the IP of the medications the patient uses, before, during and after the study. They must be registered in the corresponding section in the CRF, including name of active substance, posology and duration. See: 6.3.3 Treatments and concomitant interventions allowed and prohibited before and during the study.
- Evaluation of adverse events: see 6.4.3.3 Evaluation of adverse events
- Subject's daily delivery: refers to the delivery by the IP, of the subject's daily instrument, to the subject.

6.5.2.2 Visit 1.

- Comprehensive ophthalmologic exploration: see 6.5.2.1 Baseline visit.
- Biomicroscopy: see 6.4.3.1 Biomicroscopy
- Visual capacity: see 6.4.3.2 Visual capacity
- History of symptomatology: see 6.4.3.4 History of symptomatology
- Tonometry: see 6.4.3.6 Tonometry
- Evaluation of concomitant medications: see 6.5.2.1 Baseline visit.
- Evaluation of adverse events: see 6.4.3.3 Evaluation of adverse events
- Continuity assessment: refers to the determination by the IP and desire of the subject to continue with their participation in the study.
- Adherence evaluation: refers to the review of the subject's diary to evaluate the drug application registry.

6.5.2.3 Visit 2.

- Comprehensive ophthalmologic exploration: see 6.5.2.1 Baseline visit.
- Biomicroscopy: see 6.4.3.1 Biomicroscopy
- Visual capacity: see 6.4.3.2 Visual capacity
- History of symptomatology: see 6.4.3.4 History of symptomatology
- Tonometry: see 6.4.3.6 Tonometry
- Evaluation of concomitant medications: see 6.5.2.1 Baseline visit.
- Evaluation of adverse events: see 6.4.3.3 Evaluation of adverse events

- Continuity assessment: see 6.5.2.2 Visit 1
- Adherence evaluation: see 6.5.2.2 Visit 1

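### The two central retinal thickness objectives credit only a decrease, arm by arm, so preventing thickening would not count as efficacy in eyes with no excess thickness at the baseline scan

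*Combined protocol and SAP*

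**What the plan says.** Section 5.5.3 has one objective on central retinal thickness (GCR) for each arm. For the test product it reads "Evaluate the efficacy of PRO-145 by decreasing the central thickness of the retina (GCR". For the comparator it reads "Evaluate the efficacy of prednisolone acetate 1% by means of the decrease in GCR". Neither objective mentions the other arm.

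Section 6.2.2.2 lists "Macular diseases" among the exclusions, together with "Time > 24 hours after having surgery". Section 6.5 says the baseline visit "should be within the first 24 postoperative hours" and has the subject "start the application of the investigational products that same day". Section 6.5.2.1 adds for the tomography: "For this visit, the OCT can be done in a window period of 48 hours". The schedule in section 6.5.1 has one further scan, at the final visit on day 29 (+3). No preoperative scan is planned.

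The rationale in section 5.1 states: "Persistent inflammation causes discomfort to the patient, increased rate of macular edema and compromises the visual result".

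Section 6.4.2.2 lists central retinal thickness as a secondary efficacy variable without a direction. Table 5 makes it continuous, in microns. Section 6.4.3.5 requires both scans on the same device. Section 8.3.1 plans an inter-group t test for continuous variables, described as paired, and an intra-group McNemar test.

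**The concern.** A decrease suits the other signs in section 5.5.3. Cells, flare, hyperemia and corneal edema are expected to be present just after surgery and to clear. The retina is different in the protocol's own account: the harm is macular edema, which is thickening, and the benefit to look for is that it does not develop. Eyes with macular disease are screened out, so an eye may well enter with no excess thickness to lose.

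For such an eye the best outcome is no change, and the objective gives no credit for it. If both steroids protect equally well, neither arm shows a decrease and the arms do not differ, so the report could say that neither drug had retinal efficacy. If thickness rises modestly in both arms, neither per-arm objective is met, even if one drug limited the rise more.

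A smaller matter concerns the baseline value. Drops start on the day of the baseline visit, while the scan has 48 hours. Nothing requires the scan to come first, so a late one may be an on-treatment value.

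**Working it through.** The plan gives no figure for central retinal thickness: no expected value, SD, change, threshold or success rule. There is nothing of its own to reproduce, so the check is first a reading of the text and then an illustration.

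**Reading the text**

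1. Criterion: a decrease, stated separately for each arm (5.5.3). No other success criterion for this variable appears.
2. Entry: macular disease excluded, and no more than 24 hours since surgery (6.2.2.2).
3. Measurement: one scan near postoperative day 1 and one at day 29 (+3) (6.5, 6.5.1). Change is final minus baseline.
4. Harm named: macular edema with persistent inflammation (5.1), so a positive change.
5. Hence, for an eye without excess thickness at baseline, full protection gives a change of 0, which is not a decrease.

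**Baseline timing**

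The plan does not say from what point the 48 hours run. Counted from surgery, the scan is at most 48 hours postoperative. Counted from a visit held 24 hours after surgery, it could be 24 + 48 = 72 hours postoperative. Section 6.5 asks for four applications on day 1, or at least two if four do not fit, and section 6.3.1 for four a day after that. By the end of day 2 a subject may have had 2 + 4 = 6 to 4 + 4 = 8 drops.

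**Illustration**

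Assumptions, none of them from the plan: normally distributed change; SD of change 15, 20, 30 or 40 microns, equal in both arms; two-sided 0.05; a one-sample test of mean change within an arm; an independent two-sample test between arms. The 74 eyes per arm is the number before the loss allowance in section 6.6.1. It was set for anterior chamber cells and is used here only as a count of eyes.

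Within an arm, with true mean change μ:

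P(significant decrease) = Φ(−1.96 − μ / (SD/√74)), where √74 = 8.60.

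- μ = 0 (thickness held stable): Φ(−1.96) = 2.5% at every SD. Half of the eyes would show some decrease by chance.
- μ = +5, SD 40: 5/4.65 = 1.075, and Φ(−3.035) = 0.12%.
- μ = +5, SD 30: 0.034%. SD 20: 0.002%. SD 15: below 0.001%.

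Between arms, with 10 microns less thickening in one arm (for example +5 against +15):

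Power = Φ(10 / (SD·√(2/74)) − 1.96), where √(2/74) = 0.1644.

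| SD of change | Standard error | Power |
|---|---|---|
| 15 | 2.47 | 98% |
| 20 | 3.29 | 86% |
| 30 | 4.93 | 53% |
| 40 | 6.58 | 33% |

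So an arm with a mean rise of 5 microns against 15 in the other would almost never show a decrease of its own, yet could show its advantage in a between-arm test. If both arms have zero mean change, a significant decrease appears in at least one arm with probability 1 − 0.975² = 4.9%, and a significant difference between arms with probability 5%. Equal protection is thus invisible on both counts except by chance.

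**The case against.** The strongest reply is that only the wording of the objectives has a direction. The variable itself is a continuous measure in microns with no responder rule, section 5.6.1 says the trial will compare the two products, and section 8.3.1 plans an inter-group test. Less thickening in one arm would show there. This stands. A reader might infer that a protective drug would be scored as ineffective, but the plan contains no scoring rule that would do so. Nor is a usable within-arm test of a fall in microns specified, since McNemar needs a binary outcome and no cut-off is given.

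A reader might also infer that the direction is wrong for practically every enrolled eye, or that a decrease could arise only from measurement noise. The documents do not support this either. Excluding macular disease does not exclude thickening caused by the operation. The baseline scan is postoperative, and section 5.1 gives no time course. Some eyes may start thickened and then improve.

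New macular edema would not go unseen. Section 6.5.2.1 includes the posterior segment in the examination done at each visit, and adverse events and visual capacity are safety outcomes. The 48-hour window applies to both randomised arms, and no bias from it can be quantified.

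The reply does not remove the point. The objectives are per arm and ask for no comparison. Both arms receive a steroid, so equal protection yields neither a decrease nor a difference. The inter-group test is described as paired although the arms are independent; that is a separate defect, but it makes the rescue less secure.

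**Conclusion.** The point holds in a limited form. As worded, the two objectives recognise only a decrease in central retinal thickness within each arm. For eyes without excess thickness at the baseline scan, preventing the harm that the protocol itself names would not count as efficacy. How many eyes this covers, and by how many microns, cannot be derived from the documents. The 2.5% and the powers above rest on assumed SDs and on a within-arm test that the plan does not specify. The zero-change result does not depend on the SD.

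This affects the interpretation of one secondary variable. The primary outcome and the sample size are untouched. It should be corrected because the change is cheap and the present wording could lead to a misleading statement about either drug. The possible on-treatment baseline scan is a real but secondary weakness.

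**What to change.** Replace the two objectives with one: *compare PRO-145 with prednisolone acetate 1% on the change in central retinal thickness, in microns, final visit minus baseline, a smaller increase or a larger decrease being favourable*. Analyse it as a comparison of independent arms, keeping the same-device rule of section 6.4.3.5. Report each arm's mean change with a confidence interval, so that stable thickness in both arms is visible as such. As a supportive measure, report the proportion of eyes in each arm that thicken beyond an amount fixed before unblinding. The documents give no such amount, so the sponsor has to choose and justify it.

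For the baseline scan, state from what point the 48 hours are counted and record the scan time relative to the first study drop. Take the scan before the first drop where possible. Flag later scans, or repeat the analysis without them as a sensitivity check.

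The cost is the wording of two objectives and one outcome definition, slightly tighter scan scheduling, and one small extra analysis. No visits, scans or subjects are added.

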5.5.4 Hypothesis

H0: The use of the ophthalmic emulsion PRO-145 is not effective when decreasing the inflammatory response evaluated by means of cellularity in the anterior chamber, after phacoemulsification.

Ha: The use of the ophthalmic emulsion PRO-145 is effective in decreasing the inflammatory response evaluated by means of cellularity in the anterior chamber, after phacoemulsification.

5.6 Design and plan of the study.

Phase III clinical trial, parallel, controlled, randomized, double blind. Participants will be postsurgical phacoemulsification patients, who will be randomly assigned to 2 intervention groups with steroidal anti-inflammatory drugs. One group will receive the PRO-145 test formulation and the other group will be exposed to prednisolone acetate 1%.

[figure not shown]

Figure 2. Study design.

5.6.1 Discussion of the study design.

In clinical research it is common to propose trials with the objective of evaluating the efficacy of a product under investigation against a reference medicine or active control, in order to compare the new product under investigation from a clinical or statistical point of view to a drug commercially available

The clinical trial is the ideal model to evaluate the effectiveness of two interventions, it allows obtaining the highest quality evidence among different types of research. The characteristics of randomization and double blind, allow to avoid biases (selection, evaluation, etc.) that can not be avoided with other models. Being controlled and parallel groups allows distinguishing the effects of interventions in isolation.

The proposed clinical trial aims to evaluate the efficacy, safety and tolerability profile of a formulation of DFBA 0.05% and compare it against the safety, tolerability and efficacy profile of commercially available steroid administration, and widely used for its efficacy profile and known security.

6. Material and methods. Participants, interventions and variables.

6.1 Study Center.

The present study will be performed in ophthalmology offices duly equipped and registered for their proper functioning. According to the needs of the sponsor, these may be private or public, be attached to a hospital or clinic or be independent.

This is a multicentre study that is intended to be carried out in Guadalajara, Mexico City and Monterrey.

6.1.1 Organization of the center.

Each study center will have a principal investigator (IP). The IP is the leading ophthalmology specialist in the clinical study.

The IP is responsible for forming a multidisciplinary research team to carry out the clinical study according to protocol, under its scientific guidance. It is the prerogative of the IP the design of the organization of its center and the selection of the personnel that will perform the functions. Notwithstanding, the minimum organization of the research team requested by the sponsor requires the figure of sub-researcher, study coordinator and pharmacist.

[figure not shown]

Figure 3. Minimum organization of the center.

Any person to whom the IP designates, under his / her responsibility, a part of the follow-up of the study (co-investigator, sub-researcher, nurse, etc.) or a specific function of participation in the study (pharmacist, administrative assistant, study coordinator, etc.) It must appear in the "Delegation of Responsibilities" format.

The "Delegation of Responsibilities" and the "Organizational Chart of the Center" must be delivered to the sponsor before the start of the study and updated if the members or their responsibilities are changed.

6.1.2 Documentation to be delivered to the sponsor.

The IP must be delivered to the sponsor, before the start of the study:

- Curriculum vitae updated, in Spanish, dated and signed (maximum 10 pages), of the IP and the staff that integrates its organizational chart of the center.
- Copy of IP academic certifications (degree certificate and specialty diploma in ophthalmology, federal professional certificates)
- Copy of academic certifications of the maximum degree obtained, from each one of the members of your research team, that cover their capacity to perform the delegated functions.
- Copy of operating notice or similar issued by corresponding regulatory entity (When applicable)
- Certificate of good clinical practice in force. If the issuing institution does not specify the validity period in the certificate, the date of issue of the certificate must not exceed one year.

6.1.3 Closure of the center.

The closing of the center will be carried out once the last visit of the last included subject previously agreed between the sponsor and the IP has been made. The closing process will be according to the internal operating procedures of the sponsor.

It is the sponsor's prerogative to prematurely close a study center, it must inform the IP the reasons for the closure.

6.2 Eligibility criteria.

6.2.1 Inclusion criteria.

- Signed informed consent.
- Age ≥ 18 years.
- Both sexes.
- Postoperative cataract surgery by phacoemulsification.
 - o That they have met the criteria for phacoemulsification and a classification of the LOCS III cataract of NO ≥ 2 and NC ≥ 2 .

6.2.2 Exclusion criteria.

6.2.2.1 General criteria.

- Pregnant women, lactating or planning to get pregnant.
- Women of reproductive age and who do not have a hormonal contraceptive method, intrauterine device or bilateral tubal obstruction.
- Participation in another clinical research study ≤ 30 days before the baseline visit.
- Have previously participated in this same study with the contralateral eye.
- That they can not comply with their attendance at appointments or with all the requirements of the protocol.

6.2.2.2 Medical and therapeutic criteria.

- Surgery in both eyes in the same surgical shift.
 - Time > 24 hours after having surgery.
 - LIO placement outside the bag.
 - Presentation of rupture of the posterior capsule, with or without the presence of vitreous.
 - Carrying out an iridectomy, or lesion of the pupillary sphincter during phacoemulsification surgery.
 - Scheduled for surgical intervention in the contralateral eye during the study period.
 - History of glaucoma or ocular hypertension.
 - History of increased PIO with the use of steroids.
 - PIO ≥ 24 .
 - History of uveitis.
 - Presence of corneal abrasion or corneal ulceration in the study eye.
 - Use of steroids or topical NSAIDs, 24 hours prior to surgery and until the start of instillation of investigational drugs.
 - Use of anticoagulants, systemic steroids or immunomodulators in the last two weeks
 - Periocular injection of any steroid in the study eye 4 weeks before the start of the instillation of the investigational drugs.
 - Use of storage steroids 2 months prior to the start of instillation of investigational drugs.
 - Presence or suspicion of keratitis and / or viral, bacterial or fungal conjunctivitis.
 - Presence or suspicion of endophthalmitis.
 - Presence or suspicion of toxic syndrome of the anterior segment.
 - Severe corneal edema that does not allow assessment of the anterior chamber
 - Macular diseases.
-
- Diabetes Mellitus with A1C $\geq 6.5\%$ (48 mmol / mol) or fasting glucose (no caloric intake by ≥ 8 hours) of ≥ 126 mg / dL (7.0 mmol / L).
 - Any disease or condition that requires the use of topical or systemic NSAIDs during the time of intervention.
 - Any disease or condition that requires the use of steroids other than topical ophthalmic application.
 - Subjects with a single eye.
 - Any condition or disease that at the discretion of the IP does not make the subject suitable for the study.
 - Known hypersensitivity to the components of the products under investigation.

6.2.3 Elimination criteria.

- Decision of the subject. The subject can decide unilaterally to withdraw from the study at any time, should inform the IP.
- Pregnancy.
- Presence of a serious adverse event (EAS).
- Investigator's decision:
 - o Due to the presence of an AD that at the discretion of the IP threatens the health of the subject and requires the prescription of a medicine not authorized in the protocol
- Any deviation to the protocol that affects the safety of the subject.

6.2.4 Identification of the subject.

The patients of the study will be identified by a number and the initials of their name.

The initials of the study subject will be obtained by starting with the first letter of the name, followed by the first letter of the first surname and the first of the second, obtaining maximum three letters, in case the person has two names or a compound surname will always be used the first letter of the first name or last name composed.

Example:

1. Adolfo Daniel Mercado Carrizales

to. Initials: AMC

2. Juan De la Torre Orozco

to. Initials: JDO

[figure not shown]
3. Luis Carlos Pérez-Gómez Ramírez

to. Initials LPR

In the counting stage, the participant number will be assigned consecutively, using 3 consecutive digits. Once the subject has been selected, he will be assigned a number with which he will be identified throughout the study. Said code will be composed of eight numbers in the following order from left to right:

- three digits of the molecule under study according to the denomination by the sponsor.
- two digits corresponding to the research center number
- three digits of the number consecutive to their inclusion assigned in the research center.

Example:

6.3 Intervention .

6.3.1 Managed treatments.

The treatments will be administered four times a day, every 4 hours during the waking period, the first 14 days; later it will be completed with 14 days of application in a dose reduction scheme, this scheme will be at the discretion of the IP. The suggested schedule for applications four times a day is at 9:00 am (09:00 am), 1:00 pm (1:00 pm), 5:00 pm (5:00 pm) and 9:00 pm (9:00 pm).) for 14 days. Interventions will only be applied in the postoperative eye.

6.3.1.1 Treatment in study.

- PRO-145 .
 - Active ingredients: Difluprednate 0.05%
 - Pharmaceutical form: ophthalmic emulsion.
 - Prepared by: Sophia Laboratories, S.A. of C.V.
 - Dosage: 1 drop 4 times a day during the period of vigil in the operated eye, for 14 days. Dose reduction for 14 days at the discretion of the principal investigator.
 - Description of the emulsion: white to slightly yellow emulsion.
 - Description of container: sterile multi-dose bottle.
 - The product has certificates of sterility and stability, which are in the master folder of the study, and its characteristics are included in the researcher's manual.

Table 4. Quali-quantitative formulation of PRO-145.

Active principle	Quantity	%	Function
Difluprednate	mg / dL	0.05	Anti-inflammatory
Additives	0.50	%	Function
Castor oil	Quantity	Not shown	Not shown
Polysorbate 80	Not shown	Not shown	Not shown
Disodium edetate dihydrate	Not shown	Not shown	Not shown
Glycerin	Not shown	Not shown	Not shown
Citric acid	Not shown	Not shown	Not shown
Benzalkonium chloride	Not shown	Not shown	Not shown
Sodium hydroxide	Not shown	Not shown	Not shown
Sodium citrate dihydrate	Not shown	Not shown	Not shown
Hydrochloric acid	Not shown	Not shown	Not shown
Water for cbp injectable preparation (1)	Not shown	Not shown	Not shown

Qualitative composition of the formulation PRO-145. The agents that constitute the active substance and the additives are shown. Pharmaceutical form: emulsion. (1) How much is enough to

6.3.1.2 Reference treatment.

- Prednefrin® SF .
 - Active ingredients: prednisolone acetate 1%
 - Pharmaceutical form: Ophthalmic suspension
 - Prepared by: Allergan, S.A. of C.V.
 - Dosage: 1 drop 4 times a day during the period of vigil in the operated eye, for 14 days. Dose reduction for 14 days at the discretion of the principal investigator.
 - Description of suspension: whitish suspension.
 - Description of the container: 5ml multi-dose dropper bottle.

- The data on characterization of the reference product will be taken from the insert.

6.3.2 Strategies to improve adherence and procedure to monitor adherence.

Adherence to the intervention is essential to achieve the objectives of clinical research, adherence is defined as: "the extent to which the behavior of people (including taking medication) corresponds to the indications of the provider of services of health "[54] Effective treatments could be interpreted as ineffective due to poor adherence.

Strategies:

- At each visit, the IP reaffirms in the research subject the importance of following the indicated regimen and will ask if it has had any inconvenience in following the indications, if necessary it will retrain the subject in the application of the medications.
- In case the IP considers it necessary, the subjects that have an email, the IP or the person designated for this, will send them emails to remember the adherence to the treatment and the importance of it. The content of the emails will be previously submitted to the research ethics committee for approval.
- By means of the revision of the daily tool of the subject.

Procedure to monitor adherence:

For more than four decades, numerous investigations have been conducted on the proper way to measure and quantify adherence to medications, nevertheless none has reached consensus to establish itself as the gold standard, both in cross-sectional and longitudinal studies. [55] [56] [57] [58] [59] [60] [61] [62]

There are different procedures to measure the adherence of pharmacological interventions. The most common procedure includes self-reports, these include: patient interviews, questionnaires and self-monitoring journals. Its strengths are speed, flexibility, low cost and ease of implementation; they have a high degree of specificity for non-adherence, nevertheless the sensitivity and reliability for adherence is low. [62] [63]

The biochemical measurement of the drug, or its metabolite, is one of the methods that best confirms the use of the drug. Nevertheless, in addition to raising costs and being impractical, it is of little use in the context of ophthalmic applications, since concentrations at the peripheral level could be undetectable; and samples from other tissues imply more invasive methods that would not be advisable. [62]

Medication counting is another way to measure adherence. Classically referred to as "pills counting", in ophthalmology it is translated to the weight of the bottle. This is a simple, economical and non-invasive method. The main disadvantages of this method are: 1. The application of the medication can not be confirmed (it could have been intentionally thrown or instilled outside the eye) and 2. It depends on the subject bringing the medication back. [62] [63]

The approach with multiple procedures for measuring adhesion is recommended. Because there is no ideal adhesion measurement, it is appropriate to use more than one method when trying to achieve results that resemble reality. Selecting two or more methods allows their strengths and weaknesses to be compensated, in order to more reliably capture adherence levels. [61]

- The evaluation of the adherence by means of the diary of the subject will be carried out in the following way:

$$Ad = (A_r)100/A_i$$

Where:

Ad = Adherence

Ar = Applications registered in the first 14 days of treatment.

Ai = Applications indicated for the intervention in the first 14 days of treatment.

At the sponsor's facilities, the bottles will be weighed at the beginning and at the end of the study. The adhesion will be calculated considering: the weight of the empty bottle, the weight of the drop, the weight of the bottle with the content, the calculation of the total of drops to be applied during the entire time of intervention and the total weight of the drops applied. The following simplified formula will be used:

$$Ad = \frac{(P_i - P_f)100}{P_T}$$

Where:

Ad = adhesion

IP = weight of the bottle delivered to the subject at the start

Pf = weight of the bottle returned by the subject

PT = weight of the posology indicated for the intervention.

$$P_T = (P_g)G$$

Where:

P_g = weight of the drop of the intervention, determined by the department of research and development

G = number of drops indicated for the intervention

